# 7.2.3. Sensitivity and Additional Analyses of the Primary Endpoint

Sensitivity and additional analyses on the primary endpoint will include the following:

- 1. Analyses analogous to the primary will be run on the PP population.
- 2. Sensitivity analyses will be performed to assess the robustness of the conclusions under different assumptions for missing data for subjects who terminated early from the study. All subjects who have a mild/moderate or severe SELENA-SLEDAI flare at their last study visit will be re-categorized as experiencing clinically significant disease reactivation. Additional sensitivity analyses may be performed including single and multiple imputation methods.
- 3. A sensitivity analysis will be run to assess the impact of new or increased major immunosuppressive medications as the only cause of flare and therefore meeting primary endpoint. Subjects who re-start or increase a major immunosuppressive, but have no other disease activity that would categorize them as having a mild/moderate or severe flare will be categorized as not meeting primary endpoint (which requires both a SELENA-SLEDAI flare and increased immunosuppressive activity). Analyses analogous to the primary will be run for this sensitivity analysis.

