# 8 STATISTICAL CONSIDERATIONS AND ANALYTICAL PLAN

#### 8.1 Sample Size and Power

Sample size justification will focus on the primary endpoint of disease reactivation by Week 60. We anticipate that the risk of disease reactivation will likely increase with MMF withdrawal, and recognize that the acceptable level of increased risk will be highly variable among clinicians and their patients. The planned analyses are designed to provide information to help clinicians make decisions for individual patients with varied levels of risk tolerance. To this end, we will provide the estimated risk of disease reactivation in each arm, but more importantly we will provide the % confidence that the increased risk with MMF withdrawal  $\leq a$ , where a is a specific value for acceptable increase in risk. To facilitate decisions for individual patients, we will provide a table and/or plot showing the confidence levels over a range of values for a.

In deriving an appropriate sample size, we assumed most physicians would want at least 85% confidence that the increase in risk with MMF withdrawal  $\leq a$ , for whatever value of a is selected for an individual patient. As such, we computed, under a variety of scenarios, the probability that the study would yield estimates where the confidence was at least 85% that the increase in risk with MMF withdrawal  $\leq a$  (the acceptable increase in risk). Since this probability is analogous to power for a study designed to test a hypothesis, the term "power" will be used in this discussion.

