In addition to the study size and the selected value of *a*, power depends on two unknowns: the risk of disease reactivation for patients in the MMF maintenance arm and the increase in risk for patients upon withdrawal of MMF. With respect to the former, a preliminary analysis was conducted on observational data from a subset of 49 patients in the Johns Hopkins Lupus Cohort who were on MMF for a minimum of one year. Based on these results, the probability of experiencing disease reactivation (defined for the preliminary analysis as at least one SELENA-SLEDAI-defined flare requiring additional treatment) by month 16 was estimated at 0.10 (95% CI 0.02-0.19) for subjects remaining on MMF. For the sample size and power calculations, we assumed the risk of disease reactivation in the MMF maintenance arm would be on the range of 0.05 to 0.15. There is no preliminary data on the increase in risk with MMF withdrawal, but since patients/clinicians would be more likely to consider withdrawal if the increased risk were low, we evaluated potential increases ranging from 0.05 to 0.15.

Table 8.1 presents power estimates based on simulations for a sample size of 120 eligible subjects randomized in a 1:1 to MMF maintenance or withdrawal. If all other factors are constant, power improves as **a**, the acceptable level of increased risk, increases. However, the relevance of the study results in clinical practice decreases with increasing **a**. For example, the statement, "We are 85% confident that the increased risk with withdrawal of MMF is < a = 0.20" would be useful for those patients willing to accept an increase in risk of **a**  $\ge 0.20$ , but would not be of value for a more risk-averse patient willing to accept, say, an increase in risk of only **a** = 0.10. Unfortunately, the sample size required to achieve 80%

power when  $\boldsymbol{a} = 0.10$  (or below) are not feasible for this study. For example, if  $\boldsymbol{a} = 0.10$ , then under a best case scenario, if the risk of flare is 0.05 in the MMF maintenance arm and the increase in risk with withdrawal is 0.05 (i.e. the risk with MMF withdrawal = 0.10), then the number of patients required for 80% power is 390.

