#### 8.5.5 Missing Data

Standard procedures will be used to ensure that data are as complete and accurate as possible. In analyses, a full accounting will be made for all data items. Generally, missing data will be treated as randomly missing with no data imputation. Deviations from this approach will be specified in the Statistical Analysis Plan (SAP). If data are missing for the primary endpoint, sensitivity analyses will be conducted to assess whether conclusions are robust to alternative

analytic approaches for handling these data. If data are missing for other key endpoints, sensitivity analyses could also be conducted, if deemed appropriate. Details of the sensitivity analyses will be provided in the SAP.

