# **Endpoint:**

For each subject, a yes/no variable will be assigned to indicate whether a subject has met the primary endpoint of clinically significant disease reactivation between Day 0 and Week 60, as defined above.

Subjects who terminate early from the study, and who had not previously met primary endpoint, will be handled as follows:

- 1. Subjects who do not have a mild/moderate or severe SELENA-SLEDAI flare at their last study visit will be categorized as not experiencing clinically significant disease reactivation.
- 2. Subjects who have a mild/moderate or severe SELENA-SLEDAI flare at their last study visit:
  - a. Subjects will be categorized as experiencing clinically significant disease reactivation for the following three scenarios:
    - i. Subject has a SELENA-SLEDAI mild/moderate or severe flare at the time of early termination, and a steroid increase/burst to ≥ 15 mg/day prednisone that is sustained through end of study.
    - Subject previously experienced a flare requiring either intraarticular, intra-muscular or IV steroids, or an increase/burst of steroids that was successfully tapered to < 15 mg/day within four

Version: 1.0 Page 18 of 48

<sup>1 For ALE06, prednisone > 0.5 mg/kg/day is categorized as a severe SELENA-SLEDAI flare if the duration is >2 weeks. Increases in prednisone >0.5 mg/kg/day but for ≤2 weeks will be categorized as mild/moderate SELENA-SLEDAI flares.

weeks, and is experiencing a severe flare at the time of early termination.

- iii. Subject has a SELENA-SLEDAI severe flare based on the following clinical components: SLEDAI score; New/Worse disease, and Increase in PhGA without considering prednisone or other treatments
- b. Subjects experiencing flare at the time of early termination, but who do not met the criteria in 2.a. above, will be classified as not experiencing clinically significant disease reactivation.

These cases will be re-categorized under sensitivity analyses for the primary endpoint (see 7.2.3).

The time of clinically significant disease reactivation is defined as the date of the first SELENA-SLEDAI assessment that meets (or goes on to meet) the criteria for clinically significant SLE reactivation. The time-to-event will be defined as the interval: date of disease reactivation – date of Day 0 visit. Subjects who do not experience clinically significant disease will be censored at the last visit date on study.

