Recognizing that the appropriate value of  ${\it a}$  will be highly variable among physicians and patients, a single hypothesis is not defined for this study. Alternatively the upper 1-sided (1- $\alpha$ )% confidence limit (UCL) for the observed risk difference will be computed for values of  $\alpha$  ranging from 0 to 0.99, in 0.01 increments. Note that for a given value of  $\alpha$  the computed UCL equals the value of  ${\it a}$ , at which a null hypothesis could be rejected with a Type I error rate of  $\alpha$ . Results of these computations will be tabulated and plotted.

The primary analyses of the primary endpoint will be performed on the mITT population.

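### No committed sensitivity analysis varies the later risk of early leavers without a flare, so the upper-limit curve is not tested against informative dropout in that group

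*SAP*

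**What the plan says.** Protocol 8.5.5 treats missing data as random by default, without imputation. It then makes a promise for the primary endpoint: "If data are missing for the primary endpoint, sensitivity analyses will be conducted to assess whether conclusions are robust to alternative" ways of handling the data. It leaves the detail to the SAP.

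SAP 7.2.1 sets the rule for subjects who terminate early before reaching the endpoint: "Subjects who do not have a mild/moderate or severe SELENA-SLEDAI flare at their last study visit will be categorized as not experiencing" reactivation. They are censored at their last visit. Risk by Week 60 is a Kaplan-Meier estimate with Greenwood errors. SAP 12 says this estimator was adopted to allow for that censoring. Leavers who are flaring at the last visit count as events in three listed situations and otherwise do not.

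SAP 7.2.3 lists three items:

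- Item 1 repeats the analysis in the per-protocol population.
- Item 2 recodes every early leaver who was flaring at the last visit as an event. It then adds: "Additional sensitivity analyses may be performed including single and multiple imputation methods".
- Item 3 concerns flares defined only by a new or increased immunosuppressant. It does not address missing data.

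The output that depends on all this is the curve in SAP 7.2.2, built from one-sided upper limits for the risk difference. Physicians and patients are meant to read from it the confidence that a chosen acceptable increase *a* is not exceeded.

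**The concern.** Kaplan-Meier is valid here only if, within each arm, a censored subject's later risk equals that of subjects still under observation. Item 2 does not change this for flare-free leavers, who stay censored at the same date in the primary and the recoded analysis. The optional imputation has no stated assumption, and standard multiple imputation under missing-at-random would repeat the one already made.

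Informative dropout is plausible. Treatment is open-label, and Protocol 3.1.1 accepts that this may affect the reactivation rates. Protocol 3.2 expects dropout to increase as the trial lengthens. After Week 24 scheduled visits are 8 to 12 weeks apart, so the absence of a flare at the last visit says little about the weeks that follow.

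If flare-free leavers in the withdrawal arm reactivate more often than those who stay, the estimated increase is too low and the curve too favourable to withdrawal. Events are few (SAP 12 reports 8 of the first 80), so a handful of hidden ones can move the limit.

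**Working it through.** **Inputs.** The design uses 60 per arm ("power estimates based on simulations for a sample size of 120 eligible subjects randomized in a 1:1 to MMF maintenance or withdrawal") and a one-sided 85% level ("we assumed most physicians would want at least 85% confidence that the increase in risk with MMF withdrawal" stays within *a*), so z = 1.036. The base rates are the protocol's best case: "if the risk of flare is 0.05 in the MMF maintenance arm and the increase in risk with withdrawal is 0.05", giving 3/60 and 6/60 expected events. No dropout rate is given; 5% to 20% flare-free leavers per arm is my assumption.

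**Step 1: reproduce the plan's figures.** For *a* = 0.10 Protocol 8.1 says "then the number of patients required for 80% power is 390". With unpooled variance, n per arm = (1.036 + 0.842)² × (0.10×0.90 + 0.05×0.95) / (0.10 − 0.05)² = 194, or 388 in total against 390. For the first cell of Table 8.1 (*a* = 0.15), SE = √(0.0900/60 + 0.0475/60) = 0.0479 and power = Φ(0.10/0.0479 − 1.036) = 85.4%, against 85% stated. All 22 cells agree within 2 points by this formula.

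**Step 2: censored analysis against the bounding case.** The censored figures are Kaplan-Meier with Greenwood errors, with leavers spread evenly over weeks 0–60 and events over weeks 12–60. The bounding case counts all withdrawal-arm leavers as events and maintenance leavers as event-free. Every status is then known, so the limit is RD + 1.036 × √[p_w(1−p_w)/60 + p_m(1−p_m)/60].

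| Leavers per arm | RD, censored | 85% limit, censored | 85% limit, bounding case |
|---|---|---|---|
| 3 (5%) | 0.051 | 0.103 | 0.156 |
| 6 (10%) | 0.053 | 0.106 | 0.211 |
| 9 (15%) | 0.055 | 0.110 | 0.265 |
| 12 (20%) | 0.058 | 0.114 | 0.318 |

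**Step 3: how many hidden events matter.** Each one moves the risk difference by 1/60 = 0.017. With 6 leavers per arm, *m* of the withdrawal-arm leavers reactivating and all other leavers event-free, the limits for *m* = 0 to 6 are 0.100, 0.119, 0.137, 0.156, 0.174, 0.193 and 0.211. The limit passes 0.15 at three hidden events and 0.20 at six.

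**Step 4: what hazard that implies.** Take a constant hazard giving 10% risk at 60 weeks and a multiplier *k* after exit. Expected hidden events = Σ[1 − 0.90^(k(60−t)/60)] over exits at *t* = 5, 15, …, 55 weeks.

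- *k* = 2: 0.6 events, limit 0.111
- *k* = 5: 1.3 events, limit 0.125
- *k* = 8: 2.0 events, limit 0.136
- *k* = 12.5: 2.7 events, limit 0.150
- *k* = 15: 3.0 events, limit 0.156

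The crossing is therefore at roughly 12- to 13-fold. Even if all six left on Day 0, *k* = 5 gives 6 × (1 − 0.90⁵) = 2.46 events and a limit of 0.146. With 12 evenly spread leavers (20%), the same sum at *k* = 5 gives 2.7 events and a limit of 0.150, so about five-fold is enough.

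**Step 5: other base rates and coverage.** With 6 v 12 events and 10% leavers the censored limit is 0.178. Two hidden events take the event-count limit to 0.203, past 0.20. In simulation (risks 0.05 and 0.10, 30,000 trials, constant hazards) the nominal 85% limit covers about 83% under independent censoring. If withdrawal-arm leavers have four times the hazard after exit, coverage is 80/76/68% at 5/10/20% dropout. At eight times it is 76/67/48%.

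**The case against.** A reader might infer that the upper limit is not tested against missing data at all, or that subjects who leave because of symptoms or to restart MMF go uncounted. The documents do not support either reading.

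- Flaring leavers are covered. SAP 7.2.1 counts three classes of them as events, and item 2 recodes the rest. That is a genuine not-at-random test for those with visible evidence of rising risk.
- The flare threshold is low. A SLEDAI change above 3, new arthritis, an added NSAID or a prednisone increase is each enough. New mycophenolate is itself a severe-flare criterion. Many symptomatic leavers, and MMF restarts recorded on study, are therefore already captured.
- Stopping study drug is not leaving. Protocol 5.10.1 keeps subjects who reach the endpoint or stop for toxicity in follow-up, and 5.10.2.1 seeks a full exit evaluation from those who withdraw.
- Passing 0.15 overturns no formal decision. No margin is fixed and the analyses are descriptive.

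All of this stands, and it shrinks the group at issue to leavers with no flare criterion at their last visit, including any who restart treatment only after exit. It does not close the gap for that group. The per-protocol analysis may drop some of them but gives none a different risk. The closing sentence of the early-termination rules in SAP 7.2.1, which says these cases will be re-categorized, could be read to include them. It points to 7.2.3, though, which names only flaring leavers.

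**Conclusion.** The concern holds for informative dropout among flare-free leavers, and only for them. No committed analysis varies the independent-censoring assumption in that group, although the protocol promises a robustness check and leaves the SAP to specify it.

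The size rests on assumed dropout of 5% to 20%, the protocol's most favourable event rates and evenly spread exits. The bounding case is large: 0.211 against 0.106 at 10%. Moderate departures do little to the limit in that example. Reaching 0.15 takes about a 12- to 13-fold hazard at 10% dropout, and about five-fold at 20%. With very few leavers and plausible hazards the effect is small. The documents do not show that dropout is informative or that the reported curve is wrong. What they show is that the planned analyses could not reveal it.

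**What to change.** In SAP 7.2.3 item 2, replace the optional imputation sentence with a committed tipping-point (delta-adjusted) analysis of flare-free leavers by arm:

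- Vary the post-censoring hazard of withdrawal-arm leavers from 1 up to certain event, on a grid fine enough to locate the tipping point. Multipliers of 1, 2 and 5 alone would not find it in the 10% example above.
- Include the bounding case, with withdrawal-arm leavers as events and maintenance-arm leavers event-free.
- Re-draw the confidence curve for each setting, and report the multiplier or number of hidden events at which the 85% limit passes 0.15 and 0.20.
- State the number and timing of flare-free leavers in each arm, so that readers can judge how plausible the tipping point is.

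Also clarify in SAP 7.2.1 which leavers the sentence on re-categorized cases covers.

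The cost is one SAP paragraph and modest programming, with no new data. The downside is possibly a less favourable reported range.

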#### 7.3. Secondary Clinical Disease Activity Endpoints

All secondary analyses will be conducted in an exploratory fashion with any p-values and confidence intervals presented as descriptive statistics with no adjustments for multiple comparisons. Interval estimates will be generated at the 95% confidence level. Analyses will be conducted on the mITT population and the PP population.

Version: 1.0 Page 20 of 48

# 7.3.1. Time to Clinically Significant Disease Reactivation

**Endpoint**: See Section 7.2.1, *Computation of the Primary Endpoint*, for details on the definition of clinically significant SLE reactivation.

The time of clinically significant disease reactivation is defined as the date of the first SELENA-SLEDAI assessment that meets (or goes on to meet) the criteria for clinically significant SLE reactivation. The time-to-event will be defined as the interval: date of disease reactivation — date of Day 0 visit. Subjects who do not experience clinically significant disease will be censored at the last visit date on study.

**Analysis**: Time to disease reactivation will be summarized by treatment group. Kaplan-Meier curves will be created for each treatment arm and will include 95% confidence intervals based on the Greenwood method. Estimated percent probability of disease reactivation will be calculated at Weeks 12, 24, 36, 48 and 60. Analyses will be conducted on the mITT population and the PP population.

# 7.3.2. Probability of Experiencing a SELENA-SLEDAI Flare

**Endpoint**: The SELENA-SLEDAI instrument will be completed at baseline and every follow-up visit, including any Flare or Endpoint visits, during the course of the 60 week study period for all subjects. The SELENA-SLEDAI assesses SLE disease activity and flares based on changes in the SLEDAI score, the Physician's Global Assessment (PGA), medication use (prednisone, NSAIDS, Plaquenil, major immunosuppressives), other disease activity criteria, and hospitalization due to SLE. See Section 7.2.1., *Computation of the Primary Endpoint*, for more information on scoring of the SELENA-SLEDAI flare assessment.

For each subject, a yes/no variable will be created to indicate whether a subject had at least one mild/moderate or severe SELENA-SLEDAI flare by Week 60 and separately whether the subject had at least one severe SELENA-SLEDAI flare by Week 60. Subjects who terminate early from the study prior to experiencing any SELENA-SLEDAI flare will be categorized as not experiencing any SELENA-SLEDAI flare by Week 60.

Additionally, for each subject, the total number of visits with mild/moderate or severe SELENA-SLEDAI flares will be tabulated, including categorizing number of flare visits for a subject into 0, 1, or >1 flare.

The probability of experiencing any SELENA-SLEDAI flare and the probability of experiencing any severe SELENA-SLEDAI flare by Week 60 will be calculated in aggregate and within subgroups defined by disease manifestation (renal disease/extra-renal disease) and by baseline MMF dosing group (<2000 mg per day / ≥ 2000 mg per day).

**Analysis**: Analyses analogous to those specified for the primary endpoint (effect estimates and 95% confidence intervals, risk difference, and summaries of increased risk ( $\alpha$ ) vs.% confidence the "true" risk is  $\leq \alpha$ ) will be performed for the probability of experiencing any SELENA-SLEDAl flare and any severe SELENA-SLEDAl flare by Week 60, including analyses within subgroups for disease manifestation and baseline MMF dose. See Section 7.2.2, *Primary Analysis of the Primary Endpoint*, for more details on the analyses.

The total number of visits that a subject has with a SELENA-SLEDAI flare will be summarized by treatment group and overall. Summary tables detailing the reasons for mild/moderate or severe flares, along with reason for new or increased major immunosuppressives will be provided. Additionally, sensitivity analysis may be run to assess the impact of new or increased major immunosuppressives as the only cause of severe flare. Subjects who re-start

Version: 1.0 Page 21 of 48

or increase major immunosuppressives, but have no other disease activity that would categorize them as having a severe flare, will be categorized as not having a severe SELENA-SLEDAI flare and analyses would be replicated using this definition of a severe flare.

The study day of flare, type (mild/moderate or severe), and number of flares for each subject will also be shown graphically over time by subject and treatment group.

#### 7.3.3. Time to First SELENA-SLEDAI Flare

**Endpoint**: The SELENA-SLEDAI instrument will be completed at baseline and every follow-up visit during the course of the 60 week study period for all subjects. The SELENA-SLEDAI assesses flares based on changes in the SLEDAI score, the Physician's Global Assessment (PGA), medication use (prednisone, NSAIDS, Plaquenil, major immunosuppressives), other disease activity criteria, and hospitalization due to SLE. See Section 7.2.1., *Computation of the Primary Endpoint*, for more information on scoring of the SELENA-SLEDAI flare assessment.

For each subject, time from Day 0 to first SELENA-SLEDAI flare and time to first severe SELENA-SLEDAI flare will be calculated in study days as: date of first flare – date of Day 0 visit. Subjects who do not experience SELENA-SLEDAI flare will be censored at their last visit date on study.

**Analysis**: Analyses analogous to those specified in Section 7.3.1, *Time to Clinically Significant Disease Reactivation*, will be performed for time to SELENA-SLEDAI flare. Additionally, sensitivity analysis may be run to assess the impact of new or increased major immunosuppressives as the only cause of severe flare. Subjects who re-start or increase major immunosuppressives, but have no other disease activity that would categorize them as having a severe flare, will be categorized as not having a severe SELENA-SLEDAI flare (i.e. categorized as a mild/moderate flare) and analyses would be replicated using this definition of a severe flare.

